#### **INNOVATIONS AND LIMITATIONS**

With the overwhelming rise in obesity in the US more and more patients will present for open surgical interventions. Thus, we need better methods to reduce wound complications and morbidity. Any decrease in wound complication rates translates into improved health costs. According to our own experience at our institution, Prevena is a very promising product. It may be instrumental in lifting a large burden of health costs related to wound infections and increased hospitalization, especially for the obese patient. We believe that this randomized controlled study we propose may pave the way for Prevena to become the standard of care in the near future.

**Innovation:** There are several innovative aspects to this proposal. First, this is the first randomized controlled study of this size to assess the effect of Prevena use on wound infection rate. Second, this is the first study to assess the use of Prevena in the obese population. While, wound infection rates are kept to a minimal in clean abdominal surgeries in normal weight adults, obese patients are particularly at risk of high infection and complication rates. In our opinion, these are the surgical patients that yield the best cost-to-benefit ratio for Prevena use. Third, this is the first study to assess the effect of Prevena use on ALL possible wound complication rates (dehiscence, delayed healing, abscess formation...etc). Fourth, we will be studying larger numbers of participants than previous human studies that have examined the use of Prevena in the past. Finally, we will be assessing the bacterial count after Prevena versus standard dressing care use. We believe that this may support stronger evidence that the Prevena system decreases wound infection rates and promotes faster and more successful healing.

**Potential Problems and Alternative Strategies:** We acknowledge that the patient may not tolerate the Prevena dressing (patient adherence) – though we received very positive results from patients we piloted Prevena on and many say that they like the way it feels. However, if at any time a patient develops an allergic reaction or is unable to tolerate the Prevena dressing (such as severe incision site skin irritation or discomfort) it will be replaced by standard gauze dressing and the patient's hypersensitive reaction will be treated according to best medical management. In such case of crossover between the two treatment groups a sensitivity analysis will be performed to decide whether the number of crossover cases will have a significant effect on the outcome of the study. However, all protocol deviation cases and secondary outcomes will be reported in our final paper.

c. Blinding, including justification for blinding or not blinding the trial, if applicable.

This is a prospective single blinded randomized clinical trial. It is blinded in order to minimize any potential bias the participants may have for or against the new Prevena in comparison to the standard of care dressing.

d. Justification of why participants will not receive routine care or will have current therapy stopped.

All participants will receive routine care and will not have current therapy stopped.

e. Justification for inclusion of a placebo or non-treatment group. Not applicable

f. Definition of treatment failure or participant removal criteria.

In case of intolerance or development of an allergic reaction (such as severe incision site skin irritation or discomfort) it will be replaced by standard gauze dressing and the patient's hypersensitive reaction will be treated according to best medical practice.

g. Description of what happens to participants receiving therapy when study ends or if a participant's participation in the study ends prematurely. **Not applicable** 

# 2. Inclusion/Exclusion Criteria

#### Inclusion criteria:

1. Must be at least 18 years of age.

2. Patient has been informed of the nature of the study, and has provided written informed consent, approved by the appropriate Institutional Review Board (IRB) / Medical Ethics Committee (MEC) of the respective clinical site.

- 3. Patient meets the criteria for and is undergoing open surgery at Johns Hopkins Medical Institutes.
- 4. Patient with BMI $\geq$  30 at the time of surgery
- 5. Patient agrees to return for all required clinical follow up for the study.

# **Exclusion criteria:**

- 1. Known allergic reaction to acrylic adhesives or silver.
- 2. Known history of intolerance to any component of Prevena Incision Management SystemTM.
- 3. Very fragile skin around incision site.
- 4. Bleeding disorder or refuses blood transfusion.
- 5. Malignancy or other condition limiting life expectancy to <5 years.

6. Pregnancy.

# 3. Drugs/ Substances/ Devices

a. The rationale for choosing the drug and dose or for choosing the device to be used.

Obese patients (BMI≥30) undergoing open surgery procedures will have decreased surgical site infection rates, improved healing time, better quality of life (QOL) and lower readmission rates with use of Prevena in the post-operative management of surgical incisions.

- b. Justification and safety information if FDA approved drugs will be administered for non-FDA approved indications or if doses or routes of administration or participant populations are changed. **Not applicable**
- c. Justification and safety information if non-FDA approved drugs without an IND will be administered. **Not applicable**

# 4. Study Statistics

a. Primary outcome variable: Postoperative surgical site infection incidence

# b. Secondary outcome variables:

- 1. Other wound complications (such as dehiscence, seroma and hematoma)
- 2. Skin bacterial count after treatment

- 3. Wound healing time
- 4. Quality of life scores (SF-36 or VQL)
- c. Statistical plan including sample size justification and interim data analysis.

Power and sample size were calculated using SamplePower 2, alpha set at .05, and power of at least 80%. Current literature values suggest a similar SSI rate of 17-24%.(14, 15)

The use of Prevena has been tested in a small retrospective study (52 Prevena devices) of groin incisions in vascular surgery that yielded a large difference of 24% in SSI rates (Prevena 6%, Non-Prevena 30%).(15) Another retrospective study of Prevena use in plastic surgery showed a difference of 17% in SSI rates in patient groups receiving skin grafts (Prevena 3%, Non-Prevena 20%).(14) However, to this date the use of Prevena has not been documented in obese patients.

For a difference of 24% between control and Prevena groups, 27 patients per group (N=54) are needed to achieve power of 80%. Decreasing the group difference to 20% requires 39 patients per group (N=78) for power of at least 80%. Decreasing the group difference even further to 17% requires 54 patients per group (N=108) for power of at least 80%. To detect a smallest difference of 17%, we estimated the need for a total of 108 patients to be enrolled in this study.

- d. Early stopping rules.
  - 1. Inability to tolerate the Prevena Wound VAC
  - 2. Allergic reaction to the Prevena Wound VAC
  - 3. Evidence of wound infection during the use of Prevena Wound VAC
  - 4. Fever of >38.0 during the time the Prevena Wound VAC is in place (the wound VAC should be removed and infection of the skin ruled out)
  - 5. Statistical evidence that the Prevena Wound VAC has better outcomes versus the standard of care wound dressing\*

\*we will carry out a review of the outcomes every 6 months in this study

In order to alleviate the possibility of diabetes and smoking influencing a patient's wound healing outcomes, we stratified our randomization groups into 4 strata:

- 1) Diabetic Smoker
- 2) Diabetic Non-smoker
- 3) Non-diabetic Smoker
- 4) Non-diabetic non-smoker

Given our sample size we ran the randomization schemes for up to 60 patients in each strata.

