# Postoperative wound management

As it will be stated and agreed upon in the informed consent, the dressings in both groups will be removed on post-operative day(POD) # 5-7 (or sooner if redness or signs of infection are noted), by the provider/research coordinator in the clinic or on the ward if they are an inpatient. Then the provider/research coordinator will repeat the swabbing procedure mentioned above. Once swabbing is complete, an NP or a PA who are blinded to the study, will come in and asses the wound for healing, infection and other complications.

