# 5. Risks

a. Medical risks, listing all procedures, their major and minor risks and expected frequency.

Generally speaking there is minimal risk in participating in this study. If the patient is randomized to the standard of care they will receive our Centers standard of care for incisional wounds. If the patient is randomized to the Prevena incisional wound VAC system they may experience the following:

- 1. Discomfort and inability to tolerate the incisional wound VAC system: In this situation the dressing will be inspected by the Principle Investigator or wound nursing team who will ensure that the VAC system is properly placed and working correctly. In the event that the patient is still unable to tolerate the device, it will be removed and the patient will be excluded from the study.
- 2. Skin abrasion or irritation: If on inspection the skin edges at the incision appear to be red or irritated the incisional wound VAC will be removed and the incision inspected. The patient would be removed from the study.
- 3. Allergic reaction to the device: If at any time during the study the patient appears to have an allergic reaction to the incisional wound VAC device. The Principle Investigator will determine if the dressing needs to be removed and the patient will be removed from the study.Redness or erythema, fever, signs of infection: Should there be any concern for infection under the incisional wound VAC, it will be removed immediately and the incision assessed by the Principle Investigator, Nurse Practitioner or Physician Assistant. Appropriate standard of care will be initiated should the wound indeed be infected. This may include opening and draining the incision, wet to dry dressing changes and antibiotics treatment.
  - b. Steps taken to minimize the risks.

Follow standard surgical procedures and placement of wound dressing or Prevena Wound VAC.

c. Plan for reporting unanticipated problems or study deviations.

All events will be reported to the JHM IRB as required by the JHM IRB reporting guidelines posted on the JHM IRB website.

d. Legal risks such as the risks that would be associated with breach of confidentiality.

There should be no legal risks by participating in this study. None beyond those associated with routine care.

e. Financial risks to the participants.

None beyond those associated with routine care.

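### Fever leads to a written dressing removal and infection work-up in the Prevena arm only, with no blinding required, so unscheduled detection of the primary outcome differs in part between arms

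*Combined protocol and SAP*

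**What the plan says.** Four places in the protocol bear on this.

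- **Section 4 (Study Statistics), d. Early stopping rules, rule 4.** The trigger is "Fever of >38.0 during the time the Prevena Wound VAC is in place". The action is that "the wound VAC should be removed and infection of the skin ruled out". The rule mentions only the Prevena device.
- **Section 5 (Risks), a. Medical risks.** Among the things a Prevena patient may experience, the text gives: "Redness or erythema, fever, signs of infection: Should there be any concern for infection under the incisional wound VAC, it will be removed immediately", with "the incision assessed by the Principle Investigator, Nurse Practitioner or Physician Assistant". It does not ask for the assessor to be blinded. For the other arm it says only: "If the patient is randomized to the standard of care they will receive our Centers standard of care for incisional wounds".
- **Section 1 (Study Procedures), Postoperative wound management.** This is the rule common to both arms: "the dressings in both groups will be removed on post-operative day(POD) # 5-7 (or sooner if redness or signs of infection are noted"). Fever is not named. After removal the swab is repeated, and a blinded NP or PA then examines the wound.
- **Section 1 (Study Procedures), Follow Up.** Every patient is told to call the hospital if certain signs appear, and fever heads the list. No dressing removal, work-up or study assessment is attached to the call. Both arms have blinded examinations at POD 5-7 and POD 12-14, an interview at POD 1-2 and a contact at POD 30.

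The primary outcome is the incidence of SSI.

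**The concern.** The work-up that a fever sets off in the Prevena arm looks for the primary outcome itself. If one arm has a written extra occasion for that search and the other does not, the chance that an SSI is recorded depends on treatment as well as on infection. The assessor matters too. The main scheme keeps SSI diagnosis with a blinded NP or PA, whereas the Risks section allows the principal investigator to make the call when a device has just been taken off for suspected infection.

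More searching in the Prevena arm would, taken alone, tend to raise its recorded SSI rate, against the trial's hypothesis. The six-monthly outcome reviews would use the same data. There may also be a secondary effect: the post-treatment swab is tied to dressing removal, so if it is taken at an early removal its timing could differ between arms for the bacterial-count aim. The stopping rules and the Risks section do not say whether a swab is taken then.

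**Working it through.** **1. The provisions side by side**

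| Point | Prevena | Control |
|---|---|---|
| Fever named as a trigger for removal and infection work-up | Yes (stopping rule 4; Risks) | No |
| Early removal for redness or signs of infection | Yes (common rule) | Yes (common rule) |
| Told to call the hospital for fever | Yes | Yes |
| Study assessment attached to that call | None stated | None stated |
| Assessor at an unscheduled removal | PI, NP or PA, blinding not required (Risks); blinded NP or PA if the common rule is followed | Blinded NP or PA if the common rule is followed |
| Blinded examinations at POD 5-7 and POD 12-14 | Yes | Yes |

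The arms differ in the first and fifth rows. Whether the common rule's "or sooner if redness or signs of infection are noted" covers fever is open. The Risks section lists fever separately from signs of infection, which suggests the two are distinct, but the text does not settle it.

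**2. Reproducing the planned sample size**

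Inputs from section 4: SSI 20% control and 3% Prevena (the rates behind the 17-point difference), alpha 0.05, power 80%, 54 per group. The plan does not state sidedness; two-sided is assumed here.

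n = [1.960·√(2p̄(1−p̄)) + 0.842·√(p1(1−p1)+p2(1−p2))]² / (p1−p2)², with p̄ = 0.115

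= [1.960 × 0.4512 + 0.842 × 0.4349]² / 0.17² = 54.09, so 55 after rounding up, against 54 stated. The planned figure reproduces.

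**3. Illustrative loss of power**

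The documents give neither a fever rate nor a rate of extra detection. Assumed: 10% to 30% of Prevena patients have a fever before POD 5-7, and 5% to 10% of the resulting inspections record an SSI that would otherwise not be recorded. The added rate is the product: 0.10 × 0.05 = 0.5 points, up to 0.30 × 0.10 = 3 points. No matching extra detection in controls is assumed, which overstates the effect if febrile controls are also examined.

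Power = Φ{[(p1−p2)·√54 − 1.960·√(2p̄(1−p̄))] / √(p1(1−p1)+p2(1−p2))}, with p1 = 20%:

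| Added points | Prevena rate p2 | Expected Prevena SSIs (54 × p2) | z | Power, normal formula | Power, exact Pearson |
|---|---|---|---|---|---|
| 0 | 3% | 1.62 | 0.839 | 79.9% | 84.5% |
| 0.5 | 3.5% | 1.89 | 0.727 | 76.6% | 80.8% |
| 1 | 4% | 2.16 | 0.617 | 73.2% | 76.8% |
| 2 | 5% | 2.70 | 0.407 | 65.8% | 68.4% |
| 3 | 6% | 3.24 | 0.208 | 58.2% | 59.9% |

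The whole range is between 0.27 and 1.62 extra recorded infections among 54 patients. The planned Prevena event count is so small that one or two borderline diagnoses move the power noticeably.

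**The case against.** The strongest counter-case is that controls are not left without a route. A febrile control patient has been told to call, and the common rule then permits early removal and the blinded examination if signs of infection are noted. A reader might infer from the stopping rule that the asymmetry is complete and that controls have no matching step. The documents do not support that: the route exists, although it is not spelled out for fever and no study assessment is attached to the call.

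Second, the outcome is incidence, not time to infection. An SSI found a few days early in the Prevena arm would often still be evident at POD 5-7 or POD 12-14, so much of the effect is on the date of detection. What remains is borderline or transient findings, and the judgement of an assessor who may know the allocation.

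Third, the direction is not settled. The Risks section also takes out of the study those Prevena patients whose incision edges look red or irritated. If some of them would have been counted as SSIs, that pulls the Prevena rate down. A reader might infer a sure bias against Prevena, but the documents support only the weaker statement that extra search, by itself, pushes that way.

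Finally, a device-specific safety rule added to a common rule is not in itself a contradiction, and a risk section is expected to discuss the device. That stands. The difficulty is that the rule starts a search for the primary outcome, and the plan does not say how the result is ascertained or counted.

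**Conclusion.** The point holds as a partial asymmetry. Fever-triggered removal with an infection work-up is written for the Prevena arm only, and the resulting assessment need not be blinded. The shared early-removal rule, the advice to all patients and the identical scheduled blinded examinations reduce the consequence without removing it.

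The size cannot be estimated from the documents. The illustration spans a loss of 3.3 points of power (79.9% to 76.6%) at the low end and 21.7 points (79.9% to 58.2%) at the high end. It rests wholly on the assumed fever and yield rates, on the plan's 3% and 20%, on a two-sided test, and on no extra detection in controls. It shows how little margin 54 per arm leaves and is not a forecast. The change is worth making because it is cheap and protects the primary outcome. Confidence is high that the wording differs between arms and low on how much that matters.

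**What to change.** Reconcile Postoperative wound management, Follow Up, early stopping rule 4 and the Risks section so that:

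1. The events that trigger a study wound assessment counting towards SSI are the same in both arms. The text should say whether fever falls within the signs of infection in the common rule.
2. That assessment is made by the blinded NP or PA already in the plan, including when a dressing comes off early.
3. The reason for and day of every unscheduled assessment, and the day of any swab taken then, are recorded and reported by arm.

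Which events should trigger an assessment, and how the dressing is managed when they occur, is for the sponsor's clinicians. Nothing here proposes a clinical rule or asks that a safety step be dropped.

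Cost: protocol wording, and a few additional wound checks in control patients by existing staff.

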Based on the annual number of open procedures at John Hopkins Medical Institutes the investigators anticipate completing the inclusion of patients within a two-year period. Therefore, we plan to enroll a total of n = 108 patients over two years.

Each eligible patient will have an equal chance of being in either group (Prevena vs. standard dressing) regardless of age or comorbid conditions. However, at 6-month intervals a statistical analysis will compare covariates between the two groups. If there are any statistically significant differences between the Prevena/Non-Prevena groups in numbers of diabetics, smokers or immuno-compromised patients (such as being on steroids) an attempt will be made to equalize the numbers on both sides for the following 6-month period. Once randomized, the participant will undergo the specified procedure and at the conclusion of the case when the incision is closed have either Prevena vs. Standard of Care dressing applied. The dressing will be monitored over a 5 day period where it will then be removed. The participant will be followed thereafter until their sutures/skin staples are removed (Figure 1).

Each participant will be followed though POD 30-35. This time frame for follow up was chosen because:

- a. It will minimize data lost to follow up.
- b. It will maximize the opportunity for detection of infection, since the majority of SSIs are apparent by postoperative day 3-5.
- c. The standard of care at the Johns Hopkins surgical department includes a post-op check and visit 5 to 14 days following surgery.

Participants will be seen on the day of surgery, POD1-2, POD 5-7, POD 12-14, and POD 30±5 for a total of 5 encounters.

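### The 6-monthly efficacy stopping rule has no endpoint, test, boundary or adjusted final level, so the stated alpha of .05 is not controlled

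*Combined protocol and SAP*

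**What the plan says.** The stopping list in 4. Study Statistics, d has five items. The first four are events in individual patients. Only item 5 concerns the trial as a whole: "Statistical evidence that the Prevena Wound VAC has better outcomes versus the standard of care wound dressing". Its footnote sets the timing: "we will carry out a review of the outcomes every 6 months in this study".

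Section 4c is headed "Statistical plan including sample size justification and interim data analysis", but its text is only a sample size justification: "Power and sample size were calculated using SamplePower 2, alpha set at .05", with a power target of at least 80% and 54 patients per group for 20% versus 3%. It describes no interim analysis and names no test for the final one.

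The other recurring analysis is in 1. Study Procedures, b: "at 6-month intervals a statistical analysis will compare covariates between the two groups". It concerns baseline balance and sets no efficacy boundary. The same section gives the timetable ("we plan to enroll a total of n = 108 patients over two years") and the follow-up ("Each participant will be followed though POD 30-35").

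**The concern.** Item 5 authorises repeated comparison of the arms with the option to stop and claim benefit. Each such look is another chance of a false positive unless the threshold allows for it, and the plan sets no threshold. A reader applying the only stated level would use .05 every time.

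Two things are at stake:

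- **The primary SSI claim.** Without a boundary fixed in advance, a moderately small p-value at an interim, or at a final analysis after several looks, cannot be called significant at an overall .05.
- **The size of the effect.** A trial stopped at a small early look does so because the observed difference is large, so the estimate overstates the benefit.

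Item 5 also refers to outcomes in the plural, while the protocol lists SSI and several secondary outcomes. If any of them could trigger stopping, the error rises further.

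**Working it through.** **Inputs from the protocol.** Alpha .05, power at least 80%, 20% versus 3%, 54 per arm (4c); 1:1 allocation (Enrollment); reviews every 6 months (4d footnote); 108 patients over two years, follow-up to day 30-35 (1. Study Procedures, b).

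**Assumptions, because the plan is silent.** Two-sided testing, even accrual and no dropout. 24/6 = 4 looks: interims at 6, 12 and 18 months, then the final analysis. 54/4 = 13.5 per arm per period, so about 13, 27, 40 and 54 per arm.

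**1. The plan's own figure.** With a pooled rate of (0.20 + 0.03)/2 = 0.115:

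n = [1.96√(2 × 0.115 × 0.885) + 0.8416√(0.20 × 0.80 + 0.03 × 0.97)]² / 0.17² = (0.884 + 0.366)² / 0.0289 ≈ 54.1, so 55 per arm. Power at 54 is 79.9%. The plan's 54 is thus reproduced to within one patient as a fixed design with one analysis and no allowance for interim looks.

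**2. Type I error in the normal model.** Let Z_k = (X_1 + … + X_k)/√k with independent standard normal X. The rule as written, at .05 each time, rejects if Z_k > 1.96 at any interim or |Z_K| > 1.96 at the end.

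| Looks including final | Interims stop for Prevena only | Stopping in either direction |
|---|---|---|
| 3 | 7.9% | 10.7% |
| 4 | 8.8% | 12.6% |
| 5 | 9.6% | 14.2% |

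With four looks, the probability of falsely favouring Prevena is 6.3%. If interims count only patients with complete follow-up to day 35 (information about .20, .45, .70 and 1), 8.8% becomes 9.1%.

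**3. Exact binomial enumeration** at 13/27/40/54 per arm, interims for Prevena only:

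| Common SSI rate | z-test, four looks | Fisher, four looks | Fisher, final only |
|---|---|---|---|
| 10% | 8.1% | 2.6% | 1.9% |
| 15% | 8.6% | 3.7% | 2.5% |
| 20% | 8.9% | 4.3% | 2.7% |
| 30% | 9.2% | 5.0% | 3.1% |

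Fisher with stopping in either direction gives 3.3% to 7.0% over the same rates.

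**4. Several outcomes.** For independent endpoints and four two-sided looks, the error is 1 − (1 − 0.126)² = 0.24 for two endpoints and 1 − (1 − 0.126)³ = 0.33 for three.

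**5. Early-stopping bias** under the unadjusted z rule, true rates 20% versus 3%:

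| Per arm | Probability of stopping | Mean estimated difference |
|---|---|---|
| 13 | .179 | 35 points |
| 27 | .389 | 21 points |
| 40 | .207 | 16 points |

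About 77% of trials stop early. Their mean estimate is (.179 × .352 + .389 × .210 + .207 × .160)/.775 ≈ .23. At 13 per arm, 4 SSIs against 0 suffice: the difference is 4/13 = .308, the standard error √(.154 × .846 × 2/13) = .141, and z = 2.17.

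**The case against.** The strongest objection is that inflation is conditional. The plan names no test and no interim level, and with so few events at the first look Fisher's exact test would be a natural choice. It keeps the as-written rule at 2.6-5.0%. That calculation is right, and it means 8.8% is the consequence of one reading rather than a property of the plan. It does not supply control: the low figure comes from the test's discreteness, the plan does not choose Fisher, and two-sided Fisher looks reach 7.0% at an SSI rate of 30%. Fisher also leaves the bias. It stops about 57% of trials early (7% at 13 per arm), with an early mean of about 25 points.

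Three narrower points stand:

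- A very small interim p-value would survive any standard correction, so the damage falls on moderate results.
- The heading of 4c looks like institutional form text and is weak evidence of an intended interim plan.
- The cost of a boundary depends on the power method, as set out under the fix.

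The number and spacing of looks are assumed, but every z-test case with three to five looks exceeds .05.

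**Conclusion.** The concern holds. Item 5 is a trial-level efficacy rule with no endpoint, test, threshold, number of looks or adjusted final level, and no other section supplies them. The type I error of the SSI claim cannot be determined from the plan. At the only stated level it is 8.8% for the rule as written (four equally spaced looks, z-test; 8.1-9.2% exact) and 12.6% if stopping in either direction is allowed. The Fisher reading stays at about .05 or below by accident. Early stopping would also overstate the benefit, most severely at the first look. A boundary chosen after outcomes have been reviewed could not repair this, so it needs settling before the first 6-month review.

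**What to change.** **Simplest:** delete item 5 and keep the 6-monthly outcome review for safety only. The final analysis then keeps the full .05, and power is unchanged.

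**If an efficacy rule is wanted,** replace item 5 with wording such as: *Item 5 applies to SSI only, compared by a two-sided chi-squared test without continuity correction. Efficacy looks take place when about 27 and 40 patients per arm have completed day-30 follow-up, using Lan-DeMets O'Brien-Fleming-type spending with overall two-sided alpha .05: p < .003 and p < .018 at the interims and p < .044 at the final analysis.*

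The spending function is α(t) = 4 − 4Φ(2.241/√t), giving about .003 at t = .50, .019 at .75 and .05 at 1. The boundaries are Z = 2.963, 2.359 and 2.014. Exact alpha at SSI rates of 10-30% is 4.2-4.9% with interims for Prevena only and 4.4-5.2% two-sided. The 25% look is left out because its boundary (Z = 4.33) would need 11 SSIs against 0 at 13 per arm.

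**If all three 6-monthly looks are kept,** p < .001 at each interim and about p < .049 at the end gives an exact alpha of 4.9-5.1%.

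**Cost:** one paragraph.

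| Rule | Exact power, 20% v 3%, 54 per arm | Stops early |
|---|---|---|
| Single final z-test | 84.5% | none |
| Spending plan, two interims | 82.6% | 52% |
| p < .001 at three interims | 84.5% | about 12% |

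On these exact figures no extra patients are needed. By the normal approximation, which gives 79.9% for the fixed design, a four-look O'Brien-Fleming plan has about 79% power at 108, and about 111 patients (113 if the fixed design needs 110) would restore 80%. Under the spending plan, trials that stop early still overestimate the difference (mean 23 points), and the report should say so.
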